3. ABBREVIATIONS

Abbreviations pertain to the SAP only (not the TFLs).

AE	Adverse event
ALCS	Altria Client Services, Inc.
BMI	Body mass index
BOE	Biomarkers of exposure
CDARO	Clinical Data, Analysis, and Reporting Organization
CI	Confidence interval
CLIA-88	Clinical Laboratory Improvement Amendments of 1988
CO	Carbon monoxide
COHb	Carboxyhemoglobin
CPD	Cigarettes per day
CSR	Clinical study report
CV%	Coefficient of variation
ECG	Electrocardiogram
EOS	End of Study
FDA	Food and Drug Administration
FTCD	Fagerstrom Test for Cigarette Dependence
ICF	InfoMed Consent Form
ITT	Intent to treat
IVRS	Interactive voice response system
max	Maximum
MedDRA	Medical Dictionary for Regulatory Activities
mm	Minimum
N	Number of non-missing values
NE	Nicotine equivalent
NNAL	4-(methylnitrosamino)-1-(3-pyridyl)-1-butanol
PD	Pharmacodynamic
PEAE	Product-emergent adverse event
QTcB	QT interval corrected using Bazett's formula

QTcF	QT interval corrected using Fridericia's formula
SAP	Statistical Analysis Plan
SD	Standard deviation
S-PMA	S-phenylmercapturic acid
TFLs	Tables, figures, and listings

4. INTRODUCTION

This SAP has been developed after review of the clinical study protocol (dated 09 August 2013) and protocol amendment 1 (dated 20 August 2013).

This SAP describes the planned analysis of the data from this study. A detailed description of the planned TFLs to be presented in the clinical study report (CSR) is provided in the accompanying TFL shell document.

The intent of this document is to provide guidance for the statistical analyses of the data. In general, the analyses are based on information from the protocol, unless they have been modified by agreement between Altia Client Services, Inc. (ALCS) and Covance Clinical Data, Analysis, and Reporting Organization (CDARO). A limited amount of information concerning this study (eg, objectives, study design) is given to help the reader's interpretation. This SAP must be finalized prior to the lock of the clinical database for this study. Due to the need for an interim analysis, the SAP must also be finalized before the conduct of the interim analysis. When the SAP and TFL shells are agreed upon and finalized, they will serve as the template for this study's CSR.

This SAP supersedes the statistical considerations identified in the protocol; where considerations are substantially different, they will be so identified. Some additional analyses have been added for exploratory purposes. If further analyses are required to supplement the planned analyses described in this SAP, they may be performed and will be identified in the CSR. Any substantial deviations from this SAP will be agreed upon between ALCS and Covance CDARO and identified in the CSR. Any minor deviations from the TFLs might not be documented in the CSR, but will be captured in a Running Note to SAP document.

5. PURPOSE AND STUDY OBJECTIVES

5.1 Purpose

The purpose of this study is to:

- Estimate the change in biomarkers of exposure (BOE) in adult smokers using VBM-FG2 versus adult smokers not using VBM-FG2.
- Determine the appropriate cigarettes per day (CPD) reporting method for baseline measurements (for interactive voice response system [IVRS] Base line is defined as the average CPD recorded on Days 2 through 8).

5.2 Primary Objective

The primary objective of this study is to:

- Compare the differences in percent change in urinary total 4-(methylnitrosamino)-1-(3-pyridyl)-1-butanol (NNAL) from Baseline to End of Study (EOS) between adult smokers

randomly assigned to Test Group (*ad libitum* VBM-FG2 use) and Control Group (no VBM-FG2).

5.3 Secondary Objectives

The secondary objectives of this study are to:

- Compare the difference in BOE (urinary total NNAL, nicotine metabolites, S-phenylmercaptmic acid [S-PMA], blood carboxyhemoglobin [COHb], and exhaled carbon monoxide [CO]) and CPD between two methods for determining CPD during the Baseline Period:
 - Recall of average daily CPD for prior week using Past 7 Day Cigarettes Use Questionnaire (Day I).
 - Daily CPD tracking using an IVRS (7 day average of values recorded on Days 2 through 8).
- Compare the differences in percent change in urinary nicotine equivalent (NE), S-PMA, blood COHb, exhaled CO, and CPD from Baseline to EOS between adult smokers randomly assigned to Test Group (*ad libitum* VBM-FG2 use) and Control Group (no VBM-FG2).
- Compare the changes in all BOE and CPD from Baseline to EOS between Test Group and Control Group over 4 weeks.
- Characterize subgroups based on change in CPD from Baseline to EOS (no change, <50% reduction, ≥50% reduction, 100% reduction, increase) within each study group.
- Characterize subgroups based on change in total NNAL from Baseline to EOS (no change, reduction, increase) within each study group.
- Compare changes in the Fagerstrom Test for Cigarette Dependence (FTCD) from Baseline (Day 8) to EOS within and between each study group.
- Compare changes on the Quit Attempts and Quitting Intentions from Baseline (Day I) to EOS within and between each study group.

6. STUDY DESIGN

This is a randomized, controlled, open-label, parallel group, multi-center, 5-week pilot study to determine changes in BOE in adult smokers allowed *ad libitum* use of VBM-FG2 relative to adult smokers who are not allowed use of VBM-FG2. The data collected from this study will be used to estimate the variability of differences in the percent change from Baseline to the EOS in urinary total NNAL between Test and Control Groups; these findings will be used to estimate the sample size for a future pivotal study. This study will be conducted in approximately 150 adult

smokers who are considered to be in overall good health. Subjects will be randomized (based on gender, daily cigarette consumption [<20 and 20], and quit attempts [any quit attempts/no quit attempts]) to Test (allowed VBM-FG2 use) or Control (not allowed VBM-FG2 use) product in a 3:2 ratio (90 subjects randomized to Test: 60 subjects randomized to Control) with no more than a 60:40 distribution of either males or females to either group.

Screening	Baseline Period*		Product Use Period ^t			
Visit 1	Visit 2	Visit 3	Visit 4	Visit 5	Visit 6	Visit 7
Day -28 to Day -1	Day 1	Day 8±1	Day 15 ± 1	Day 22 ± 1	Day 29± 1	Day 36 ± 1
Subject evaluated against inclusion and exclusion criteria for study eligibility	Baseline CPD data gathered using recall of previous week and daily IVRS call.		Randomization in a 3:2 ratio (Test:Control) 
 • Test = ad libitum VBM-FG2 • Control = no VBM-FG2 			
Enrollment		Randomization				

*Baseline Period = after the daily IVRS call on Day 1 through the daily IVRS call on Day 8.

^t Product Use Period = after the daily IVRS call on Day 8 through the daily IVRS call on Day 36.

Note: Subjects in both groups are allowed to smoke their regular brand cigarettes during the entire study period

Expected duration of the study, from first subject first visit through last subject last visit is approximately 3 months. Expected duration for each subject is expected to be up to approximately 5 weeks (potentially 9 weeks from Screening to EOS). All subjects will be informed that they are allowed to smoke their own cigarettes or to quit smoking during the study.

Screening (Visit 1) will occur within 28 days of Day 1 (Day -28 to Day -1). An informed Consent Form (ICF) must be signed prior to conducting any study related procedures. Potential subjects will undergo an initial evaluation (vital signs, urine pregnancy test [females only], and questionnaires) to determine initial eligibility. If the subject passes the initial evaluation, then he/she will be provided with a sample of VBM-FG2 and asked to use the product as they like for 15 minutes. Subjects will then complete a Potential Purchase Interest Questionnaire. If they indicate that they "definitely would buy" or "probably would buy" the product on the questionnaire, then the subject will undergo the rest of the screening procedures (clinical labs and electrocardiogram [ECG]). Laboratory values will be evaluated by a local laboratory.

Subjects will return to the study site on the evening of Day 1 for Visit 2. A physical examination will be conducted and subjects who satisfy all the inclusion criteria and exclusion criteria will be eligible for enrollment in the study. Once a subject is enrolled in the study (Day 1), if they choose to no longer participate, they will be considered a drop-out/early termination subject.

During the Baseline Period, at Visits 2 and 3 (Days 1 and 8), blood and urine samples will be collected for analysis of BOE. Subjects will also complete the Past 7 Day Cigarettes Use Questionnaire while at the study site, to indicate their CPD over the previous week. During the Baseline Period (Days 1 to 8) subjects will report CPD daily through an IVRS.

At Visit 3, approximately 150 subjects will be randomized to either the Test or Control Group in a 3:2 ratio (with not more than a 60:40 distribution of either males or females to either group). VBM-FG2 will be dispensed to subjects randomized to the Test Group for *ad libitum* use beginning after the Day 8 IVRS.

The Product Use Period will begin following the Day 8 \pm 1 IVRS and will continue through Day 36 \pm 1. Subjects in the Test Group will be provided VBM-FG2 for *ad libitum* use. Subjects in both Test and Control Groups will continue daily tobacco use tracking via an IVRS and return to the study site once a week during the 4-week Product Use Period for Visits 4 through 7, Days 15, 22, 29, and 36, respectively. These weekly visits will include collection of urine and blood samples for BOE measurements, dispensing VBM-FG2 supplies (Test Group only, Days 8, 15, 22, 29) and return of VBM-FG2 supplies and collection of empty product packaging (Test Group only, Days 15, 22, 29, 36) as appropriate.

Subjects will be instructed to report all adverse events (AEs) and changes in concomitant medications and if necessary, to return to the study site for further evaluation. During the EOS visit (Day 36 or Early Termination), additional assessments will be performed to confirm the health and well-being of the subject.

7. STUDY PRODUCT

The VBM-FG2 discs are oral, non-dissolvable products containing tobacco-derived nicotine (approximately 1.5 mg/disc) that may provide an opportunity for adult cigarette smokers to move down the continuum of risk. These discs are a tobacco-derived nicotine product designed to appeal to adult cigarette smokers who are interested in tobacco product alternatives to cigarettes. These discs are designed to be spit-free and chewable.

Subjects in the Test Group will be provided VBM-FG2 discs and told to use them *ad libitum* throughout the study.

The groups will be presented in the TFLs as follows:

Study Group	Abbreviation
Subjects allowed ad libitum use of VBM-FG2	Test
Subjects not allowed use of VBM-FG2	Control

8. SAMPLE SIZE JUSTIFICATION

This pilot study is being conducted with an objective to collect data on the variability of the primary outcome measure, which will be used to estimate the sample size for a future pivotal study. The sample size for this study is believed to be appropriate based on statistical principles for pilot studies.

9. SAMPLE COLLECTION AND ENDPOINTS

Urine BOE (with the exception of creatinine) will be analyzed using validated analytical methods with appropriate quality controls according to the Food & Drug Administration (FDA) Guidance for Industry: Bioanalytical Method Validation (May 2001) and in accordance with FDA Good Laboratory Practice regulations (Title 21 CFR Part 58).¹² Urine creatinine and blood COHb will be analyzed at a Clinical Laboratory Improvement Amendments (CLIA)-88 certified clinical laboratory. Biomarkers of exposure will include:

Urine:

- Nicotine
- 5 metabolites of Nicotine
 - o Cotinine
 - o Trans-3'-Hydroxycotinine
 - o Trans-3'-Hydroxycotinine-O-glucuronide
 - o Nicotine-N-glucuronide
 - o Cotinine-N-glucuronide
- Total NNAL
- Urinary S-PMA

Nicotine Equivalents:

Nicotine equivalents (mg) is calculated as the molar sum of total nicotine, total cotinine, and total trans-3'-hydroxycotinine excreted in the spot urine sample.

The concentration of each metabolite is first adjusted by the spot urine volume to obtain the amount excreted in the sampling period, then divided by the molecular weight of the metabolite to obtain the amount of each in moles. The sum in moles is then converted to mass of nicotine equivalents by multiplying by the molecular weight of nicotine.

$$\text{Nicotine equivalents (mg)} = [\text{Total Nicotine (mg)} / 162.23 \text{ (mg/mmol)} + \text{Total cotinine (mg)} / 176.22 \text{ (mg/mmol)} + \text{Total trans-3'-hydroxycotinine (mg)} / 192.22 \text{ (mg/mmol)}] \times 162.23 \text{ (mg/mmol)}.$$

Adjustments of Urinary BOEs by Urine Creatinine:

For urinary BOEs (Total NNAL, Nicotine Equivalents, and S-PMA) the biomarker concentration will be adjusted by urine creatinine that was measured from the urine samples and the derived variable will be used as the analysis variables for descriptive and inferential statistics.

The following formula will be used for creatinine adjustment:

$$[\text{mass biomarker} / \text{g creatinine}] = [\text{mass biomarker/mL}] / [\text{mg creatinine/dL}] \times 10^5$$

The exponent power (5) in 10^5 will be adjusted if biomarker concentration is reported in a unit other than mass/mL, e.g. mass/dL. If a urine creatinine value is missing or outside the acceptance range (Adult males: 20-25 mg/kg/day, Adult females: 15-20 mg/kg/day), the corresponding creatinine adjusted biomarker value will be considered as missing.

Covance will use the above formula to conduct some sample calculations and submit the results to ALCS for review. Appropriate modifications will be made if deemed necessary after the review.

Blood: COHb

Respiratory: Exhaled CO

Statistical Analysis Endpoints:

- Urine Creatinine Adjusted TotalNNAL
- Urine Creatinine Adjusted Nicotine Equivalents
- Urine Creatinine Adjusted S-PMA
- Unadjusted COHb
- Unadjusted Exhaled CO
- Total FTCD Score
- CPD
- VBM-FG2 use and other tobacco product use
- Quit Attempts and Quitting Intentions

The word "Adjusted" or "Unadjusted" will not be used while referring to the above statistical analyses endpoints later on but it will be adjusted/unadjusted based on the above list. The first 5 endpoints will be referred to as 5 BOEs.

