9.1 Urine Sample Collection for Biomarker Analysis

A urine sample will be collected at Visits 2 through 7. Urine will be collected upon arrival at the study site. Participants will be instructed to not void their bladders for approximately 2 hours before the study visit. The total volumes for each urine void will be recorded.

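### Does deriving nicotine equivalents in mg per void, then applying a per-mL creatinine formula, leave void volume in the endpoint?

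*SAP*

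**What the plan says.** All the relevant rules but one are in SAP section 9.

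- **NE derivation.** "Nicotine equivalents (mg) is calculated as the molar sum of total nicotine, total cotinine" and total trans-3'-hydroxycotinine in the spot sample. Before summing, "The concentration of each metabolite is first adjusted by the spot urine volume to obtain the amount excreted in the sampling period". The printed equation takes mg and returns mg.
- **Creatinine adjustment.** "For urinary BOEs (Total NNAL, Nicotine Equivalents, and S-PMA) the biomarker concentration will be adjusted by urine creatinine". The formula divides mass/mL by creatinine in mg/dL, multiplies by 10^5, and gives mass per g creatinine. The exponent "will be adjusted if biomarker concentration is reported in a unit other than mass/mL".
- **Check.** The contract statisticians run sample calculations with this formula and send them to the sponsor. "Appropriate modifications will be made if deemed necessary after the review".
- **Endpoint.** The analysis variable is listed as "Urine Creatinine Adjusted Nicotine Equivalents".

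Section 9.1 adds the sampling rule ("Participants will be instructed to not void their bladders for approximately 2 hours before the study visit") and the record of volume ("The total volumes for each urine void will be recorded").

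**The concern.** The first rule ends with an amount (mg per void) and the second starts from a concentration (mass/mL). No sentence turns one into the other. The exponent rule does not help: it rescales by powers of ten, and no power of ten removes a volume that differs from void to void.

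If the mg value were inserted as derived, creatinine correction would no longer cancel dilution for NE. Percent change from baseline divides by a single Day 8 value (section 11.2), so the ratio of two void volumes would multiply the true ratio. Holding urine for about 2 hours standardises volume only in part. Adjusted NE is a named secondary endpoint (section 11.3.2). It also enters the Day 1 versus Day 8 paired test, the mixed models and the regressions in section 11.4.2, so all of these would be affected.

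**Working it through.** **1. The plan's factor.** 1 mg/dL = 10^-3 g / 100 mL = 10^-5 g/mL. So (mass/mL) / (mg/dL) x 10^5 = mass/g. The printed 10^5 is right for a concentration numerator.

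**2. NE with the plan's molecular weights.** The concentrations are my assumptions, for illustration only: total nicotine 2, total cotinine 2.5 and total trans-3'-hydroxycotinine 5 micrograms/mL; creatinine 100 mg/dL.

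NE = (2/162.23 + 2.5/176.22 + 5/192.22) x 162.23 = 2 + 2.30 + 4.22 = 8.52 micrograms/mL = 0.00852 mg/mL.

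Adjusted: 0.00852 / 100 x 10^5 = 8.52 mg/g creatinine.

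**3. Both printed rules followed in order, at three assumed void volumes.**

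| Void volume (mL) | NE by the SAP derivation (mg) | NE / volume (mg/mL) | Adjusted NE (mg/g) | If mg is inserted instead |
|---|---|---|---|---|
| 80 | 0.682 | 0.00852 | 8.52 | 682 |
| 150 | 1.278 | 0.00852 | 8.52 | 1278 |
| 400 | 3.409 | 0.00852 | 8.52 | 3409 |

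Dividing by the recorded volume makes the two rules fit, and the volume drops out. Dividing NE (mg) by the grams of creatinine in the same void gives the same number. At 150 mL, creatinine is 100 x 150 / 10^5 = 0.15 g, and 1.278 / 0.15 = 8.52 mg/g.

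**4. Dilution.** Take a void holding 1 mg NE and 100 mg creatinine. At 100 mL: 0.01 mg/mL over 100 mg/dL, x 10^5 = 10 mg/g. At 200 mL: 0.005 mg/mL over 50 mg/dL, x 10^5 = 10 mg/g. With mg inserted, the two results are 1000 and 2000.

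**5. Size of the error if the slip occurred.** The last column of the table equals the correct value times the volume in mL, whatever the concentrations. With exposure and urine concentrations unchanged, a void going from 100 to 200 mL would read as +100%, and one going from 200 to 100 mL as -50%. If volumes were lognormal and independent between visits (an assumption), the mean volume ratio would be 1 + CV^2. Volume CVs of 30, 50 and 70% would then add a mean spurious change of +9, +25 and +49% where the true mean change is zero.

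**6. What the text allows.** Three features of the adjustment rule point the same way: the word concentration, the mass/mL numerator and the mass per g creatinine result. An NE in mg satisfies none of them. The one quantity needed to convert it, the void volume, is collected at every visit.

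**The case for a change.** The strongest case for a change is that the only printed NE derivation does not deliver what the adjustment formula needs. Volume is recorded, so the volume step can be programmed exactly as written. The sample calculations are not required to include NE or to vary the volume, and one example at one volume might raise no alarm. The cost of a clarification is a sentence or two, with no new data.

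Part of this stands. The linking step is absent, and the sample-calculation clause does not name NE as a test case. But the text leaves only one dimensionally valid route, and it gives the correct value. The error also needs more than a literal reading, because the analyst must put an amount where the formula asks for a mass per mL. The result then carries units of mg x mL per g, and at the assumed volumes it is 80 to 400 times the correct figure. NE is one of only three biomarkers named for this formula, so a sponsor review of calculations made with it is well placed to see this.

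The precision loss under the slip cannot be sized from the SAP, which gives no spread for void volume or for NE. Any such figure would mostly reflect the assumptions put in.

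**Conclusion.** The concern does not call for a change. Section 9 omits one unit conversion between two rules that are each correct. Following the printed units gives zero error at every void volume. Inserting the mg value would multiply each adjusted NE by its void volume in mL, but only against those units and past a scheduled check. The exposure is limited to NE, a secondary endpoint in a pilot study. The SAP gives no volume-based derivation for total NNAL or S-PMA, and COHb and exhaled CO are not urinary measures, so the primary comparison and the pilot's variability aim are unaffected.

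This rests on the analyst reading the formula's units as printed and on the void volumes being recorded as section 9.1 requires. The concentrations, creatinine level, volumes and volume CVs used above are illustrative. The cancellation of volume and the proportional error do not depend on them.

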11. STATISTICAL METHODOLOGY

11.1 General

Data listings will be provided for all subjects up to the point of withdrawal, with any subjects excluded from the relevant population highlighted. Summary statistics and statistical analyses will generally only be performed for subjects included in the relevant analysis population. For the calculation of summary statistics and statistical analysis, unrounded data will be used. For continuous data, summary statistics will include the number of non-missing values (N), mean, median, standard deviation (SD), minimum (min), maximum (max). For categorical data, frequency counts and percentages will be presented.

Mean change from baseline is the mean of all individual subjects' change from baseline values. Each individual change from baseline will be calculated by subtracting the individual subject's baseline value from the value at the timepoint. The individual subject's change from baseline values will be used to calculate the mean change from baseline using a SAS® procedure such as Proc Univariate.

Mean percent change from baseline is the mean of all individual subjects' percent change from baseline values. Each percent change from baseline will be calculated by subtracting the individual subject's baseline value from the value at the desired timepoint and then dividing this calculated value by the individual subject's baseline value and multiplying by 100. These

individual subjects' percent changes from baseline values will be used to calculate the mean percent change from baseline using a SAS® procedure such as Proc Univariate.

Missing values will not be imputed.

Data analysis will be performed using SAS® Version 9.1.3 or higher.

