Least squares mean and standard error for the product effect will be estimated by study group and visit with P-values. P-values will also be provided for other effects in Model 2. While group comparison will be made on multiple visits in the model, the difference in change from baseline to the last visit will be the primary comparison and other comparisons will be secondary.

The models will be applied on both the mITT and the Per-protocol populations.

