APPENDIX 2: LIST OF TFLS FOR INTERIM AND FINAL ANALYSES

Following is the list of TFLs that will be produced during the interim analyses.

- Table 14.1-1 Summary of Subject Disposition
- Table 14.1-2 Summary of Screening Demographics
- Table 14.1-3 Summary of Baseline Smoking Characteristics
- Table 14.2.1-3.1 Individual Data and Summary Statistics of S-PMA
- Table 14.2.1-3.2 Individual Data and Summary Statistics of Change from Baseline S-PMA
- Table 14.2.1-3.3 Individual Data and Summary Statistics of Percent Change from Baseline S-PMA
- Table 14.2.1-4.1 Individual Data and Summary Statistics of Carboxyhemoglobin
- Table 14.2.1-4.2 Individual Data and Summary Statistics of Change from Baseline Carboxyhemoglobin
- Table 14.2.1-4.3 Individual Data and Summary Statistics of Percent Change from Baseline Carboxyhemoglobin
- Table 14.2.1-5.1 Individual Data and Summary Statistics of Exhaled Carbon Monoxide
- Table 14.2.1-5.2 Individual Data and Summary Statistics of Change from Baseline Exhaled Carbon Monoxide
- Table 14.2.1-5.3 Individual Data and Summary Statistics of Percent Change from Baseline Exhaled Carbon Monoxide
- Table 14.2.1-6.1 Individual Data and Summary Statistics of Cigarettes per Day
- Table 14.2.1-6.2 Individual Data and Summary Statistics of Change from Baseline Cigarettes per Day
- Table 14.2.1-6.3 Individual Data and Summary Statistics of Percent Change from Baseline Cigarettes per Day
- Table 14.2.1-7.1 Individual Data and Summary Statistics of Total Score of Fagerstrom Test for Cigarette Dependence
- Table 14.2.1-7.2 Individual Data and Summary Statistics of Change from Baseline Total Score of Fagerstrom Test for Cigarette Dependence
- Table 14.2.1-7.3 Individual Data and Summary Statistics of Percent Change from Baseline Total Score of Fagerstrom Test for Cigarette Dependence
- Table 14.2.1-X Individual Data and Summary Statistics of Urine Creatinine (Interim only)
- Table 14.2.1-8.1 Individual Data and Summary Statistics of VBM-FG2 Discs per Day

- Table 14.2.1-8.2 Individual Data and Summary Statistics of Change from Baseline VBM-FG2 Discs per Day
- Table 14.2.1-8.3 Individual Data and Summary Statistics of Percent Change from Baseline VBM-FG2 Discs per Day
- Listing 16.2.8-12 Other Tobacco or Nicotine Containing Product Use Questionnaire by Subject
- Table 14.2.1-12 Individual Data and Summary Statistics for Number of Quit Attempts with Change from Baseline

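### The rule that sets creatinine-adjusted NNAL to missing compares a spot-urine concentration (mg/dL) with a daily excretion range (mg/kg/day), so it cannot be executed as written

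*SAP*

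**What the plan says.** Section 9 divides each urinary biomarker concentration (mass per mL) by urine creatinine (mg per dL) and multiplies by 10^5 to give mass per gram of creatinine. The adjusted values are the analysis variables, and the endpoint list includes "Urine Creatinine Adjusted TotalNNAL". If creatinine is missing, or falls "outside the acceptance range (Adult males: 20-25 mg/kg/day, Adult females: 15-20 mg/kg/day), the corresponding creatinine adjusted biomarker value will be considered as missing".

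Section 9.1 describes one urine sample at each of Visits 2 to 7. "Participants will be instructed to not void their bladders for approximately 2 hours before the study visit". The volume of each void is recorded.

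Three further provisions determine what a rejected sample costs:
- Section 11.1: "Missing values will not be imputed".
- Section 11.2 makes Day 8 the baseline for all biomarkers of exposure.
- Section 11.4.1: "the difference in change from baseline to the last visit will be the primary comparison".

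Section 8 says the pilot is run to "collect data on the variability of the primary outcome measure", for sizing a later pivotal study.

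**The concern.** The range in mg/kg/day is a weight-normalised daily excretion rate. The quantity screened against it is the creatinine concentration of a single void. The two have different dimensions, and the SAP does not say how to get from one to the other. Void volume is recorded, so the creatinine amount in the void could be derived. A rate also needs body weight and the actual time since the previous void, and for the latter the SAP has only an instruction to hold for about 2 hours.

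Two programmers could therefore build different primary datasets from the same text. One might find the rule inapplicable and drop nothing, another might reject nearly every sample, and a third something in between. A rejected Day 8 value removes every change score for that subject, because Day 8 is the only biomarker baseline. The loss reaches three of the five biomarkers of exposure, including the primary one. Any sizeable loss costs precision and distorts the variability estimate the pilot exists to provide.

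**Working it through.** **Unit of the measured creatinine.** (mass/mL) ÷ (mg/dL) = 100 mass/mg, since 1 dL = 100 mL. Multiplying by 1000 mg/g gives 10^5 mass/g. The SAP's factor is reproduced exactly, which confirms that creatinine enters as a concentration in mg/dL.

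**Can the range be turned into mg/dL?** Limit in mg/dL = (mg/kg/day limit × weight in kg) ÷ (24-hour urine volume in dL). The SAP describes no 24-hour volume. For an assumed 80 kg man, 20–25 mg/kg/day becomes 160–200 mg/dL at 1 L/day and 53.3–66.7 mg/dL at 3 L/day. The two bands do not overlap, so no single cut-off follows from the stated range.

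**Can the void be turned into a rate?** Rate = (mg/dL × void volume in dL ÷ kg) × 24 ÷ collection hours. The SAP gives neither this derivation nor a recorded interval. Three readings show the possible consequences.

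1. *Void amount per kg compared directly with the range.* At the mid-range rate, a 2-hour void holds 22.5 × 2/24 = 1.9 mg/kg in men (floor 20) and 17.5 × 2/24 = 1.5 mg/kg in women (floor 15). Essentially every sample fails.

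2. *Void scaled to 24 hours with a nominal 120 minutes.* A subject excreting exactly mid-range leaves the band when the true interval is off by more than 120 × 2.5/22.5 = 13.3 minutes (men) or 120 × 2.5/17.5 = 17.1 minutes (women). No CV is needed for this result.

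3. *As in 2, with random variation.* The SAP gives no creatinine SD. Assume a normal distribution centred mid-range with a CV of 10%, 20% or 30%. Then p = P(lower limit < N(mid, CV × mid) < upper limit).

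| | CV 10% | CV 20% | CV 30% |
|---|---|---|---|
| One sample in range (p): men | 73% | 42% | 29% |
| One sample in range (p): women | 85% | 53% | 37% |
| Day 8 and at least one of Visits 4–7, p × (1 − (1 − p)^4): men | 73% | 37% | 21% |
| Same: women | 85% | 50% | 31% |
| Day 8 and Visit 7, p²: men | 54% | 18% | 8% |
| Same: women | 72% | 28% | 13% |

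With an assumed equal sex split, the second criterion keeps about 118, 65 and 39 of 150 subjects. These are the subjects who can enter the mixed model at all. Half of single samples are lost at a CV of (2.5/22.5)/0.6745 = 16.5% in men and (2.5/17.5)/0.6745 = 21.2% in women.

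**Sensitivity to the assumptions.** The table treats visits as independent. Simulated with a between-visit correlation of 0.5, entry to the model is 72%, 38% and 22% of men and 84%, 50% and 31% of women. The Day 8 and Visit 7 pair is kept by 57%, 20% and 10% of men and 74%, 30% and 15% of women. A lognormal shape in place of the normal gives single-sample rates within about one percentage point of those in the table.

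**The case against.** The strongest reply is that the SAP already has a route to repair. In Section 9, right after the rule, the contract research organisation "will use the above formula to conduct some sample calculations" and send them to the sponsor, with changes to follow where needed. The Appendix 2 interim table of urine creatinine could also bring the problem to light. Both points are fair. However, the review is of the formula, which is already correct, and the text does not mention the range. The interim table may expose the fault but does not mend it. Section 4 requires the SAP to be final before the interim analysis, so a repair made then would change an exclusion rule for the primary endpoint after data had been seen, in an open-label study.

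A second reply is that a rule nobody can execute loses nothing if the programmer stops and asks. The attrition figures also rest on invented derivations and on assumed CVs, centring and sex split, and independent visits give the lower end for the Day 8 and Visit 7 pair. This stands as a limit on the figures: they are scenarios, not forecasts. The unit mismatch and the timing tolerance depend on no CV.

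A third reply is that an excretion-rate check could be kept if the conversion were stated. That would need the actual void interval, which this SAP does not record. If the protocol captures it, the SAP would still have to set out the derivation.

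**Conclusion.** The point holds and must be fixed. A rule that decides which primary-endpoint values exist is stated in units that do not match the measurement, with no conversion. That conclusion rests on the SAP's text alone.

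The size of the loss is not determined by the document. It runs from none to nearly all samples, depending on the reading. Under the most workable reading, scaling to 24 hours on a nominal 2 hours, the tolerance is about 13 minutes for a mid-range man and 17 minutes for a mid-range woman. At an assumed CV of 20%, fewer than half of the 150 subjects (about 65) would enter the primary model. The rule is the same in both groups, so bias between them is possible but not shown. The demonstrated risk is to reproducibility, precision and the variability estimate.

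**What to change.** Before the interim analysis, amend the creatinine paragraph of Section 9 in one of two ways:

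- Delete the mg/kg/day criterion, and set an adjusted value to missing only when creatinine is missing or not quantifiable.
- Replace it with a spot-urine limit in mg/dL agreed with the laboratory in advance. State in advance whether samples outside that limit are excluded, or only flagged and examined in a sensitivity analysis. That choice is the sponsor's.

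In either case, report the number of adjusted values set to missing by group and visit. The cost is SAP wording and one count table; no new data are needed.
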